7.1 Full Analysis Set

The Full Analysis Set (FAS) includes all subjects enrolled in this study. This analysis set will be used for all final analyses.

7.2 Interim Analyses Set

The Interim Analysis Set (IAS) includes all subjects from the FAS that complete the Week 52 visit at the time of interim analysis, or discontinued study prior to Week 52.

7.3 Subgroup Analyses

Subgroup analysis of the primary endpoint will be conducted for the subgroup corresponding to each level of the following baseline variables:

- Age (< 65, ≥ 65)
- Sex
- Race (white, non-white)
- LDL-C (< median, ≥ median)
- ACC/AHA statin background therapy high intensity (yes, no)

8. Interim Analysis and Early Stopping Guidelines

There will be a 1-year interim analysis to summarize the data collected up to week 52 of all IAS subjects. There are no plans to modify or discontinue this study based on the results of the interim analysis. If required to satisfy evolocumab development program

needs, additional analyses may be performed periodically throughout the study after the parent study is closed and individual subjects are unblinded to their lipid values as required by overall evolocumab development program.

The 1-year interim analysis will summarize:

- Study and IP disposition up to week 52
- Demographics
- By-visit summary of LDL-C up to week 52
- Overall summary of treatment emergent AE/SAEs and summary by system organ class, high level term and preferred term in descending order of frequency up to week 52
- Summary of positively adjudicated clinical events up to week 52

Week 52 cutoff for disposition and adverse/clinical events is defined as the Week 52 LDL-C lab date. If Week 52 LDL-C value is missing, then use the Week 52 target day 365 as the cutoff.

9. Data Screening and Acceptance

9.1 General Principles

The objective of the data screening is to assess the quantity, quality, and statistical characteristics of the data relative to the requirements of the planned analyses.

9.2 Data Handling and Electronic Transfer of Data

The Amgen Global Study Operations-Data Management (GSO-DM) department will provide all data to be used in the planned analyses. This study will use the RAVE database.

All data collected in the eCRF will be extracted from RAVE. Protocol deviations will be transferred from eClinical. Details on data transfer will be provided in the Data Transfer Plan.

9.3 Handling of Missing and Incomplete Data

9.3.1 Patterns of Missing Data

Subjects may be missing specific data points for various reasons. In general, data may be missing due to a subject's early withdrawal from study, a missed visit, or non-evaluability of a data point or an endpoint at a particular point in time. The frequency and pattern of missing data for selected endpoints will be assessed through descriptive summaries of the measurements over time.

9.3.2 Handling of Incomplete Dates

Adverse event and concomitant medication with completely or partially missing start dates will be queried. After the issue is queried, if the date is still incomplete with year only or year and month only, the start date will be imputed as described in Table below.

Table 1. Imputation Rules for Incomplete Dates

	Missing	Imputation	Exception
Start date (AE and concomitant medication)	Day	1	Default to Study Day 1 if an event starts the same year and month as Study Day 1
	Day / Month	1-Jan	Default to Study Day 1 if an event started the same year as Study Day 1

9.4 Detection of Bias

A factor that may bias the results of the study is major protocol deviations likely to impact the analysis and interpretation of the endpoints. Important protocol deviations likely to impact the analysis and interpretation of the endpoints will be tabulated in the Clinical Study Report (CSR).

If any sensitivity analyses are required to evaluate potential biases in the study's conclusions, the sources of the potential biases and results of the sensitivity analyses will be documented in the CSR.

9.5 Outliers

Various methods, including univariate summaries, histograms, scatter plots, box plots, and line graphs, may be used to identify outliers in key safety and efficacy variables. Extreme data points will be identified during the review of the data prior to database snapshot. Such data points will be reviewed with clinical data management to ensure accuracy. Unless specified otherwise, all analyses will include outliers in the data. Sensitivity analyses may be undertaken if extreme outliers for a variable are observed.

9.6 Distributional Characteristics

There are no distributional requirements for the planned analyses.

9.7 Validation of Statistical Analyses

Programs will be developed and maintained, and output will be verified in accordance with current risk-based quality control procedures.

Tables, figures, and listings will be produced with validated standard macro programs where standard macros can produce the specified outputs.

The production environment for statistical analyses consists of Amgen-supported versions of statistical analysis software, for example the SAS System version 9.4 or later.

10. Statistical Methods of Analysis

10.1 General Principles

Statistical analyses in this open-label extension study will be descriptive in nature. No statistical inference is planned. There will be no imputation for missing data.

Subject disposition, demographics, baseline characteristics and exposure to IP will be summarized.

Summary statistics for continuous variables will include the number of subjects, mean, median, standard deviation or standard error, minimum, and maximum. For categorical variables, the frequency and percentage will be given.

One-year interim and final analyses will be based on data collected from this study. Descriptions of any integrated analyses with the parent study are out of scope for this SAP.

For all endpoints, results will be summarized by the treatment group to which subjects are randomized in Study 20120153, unless otherwise specified.

10.2 Subject Accountability

The number of subjects enrolled will be summarized by the randomized treatment groups in Study 20120153. Study, IP and background therapy discontinuation will be tabulated separately by reasons for discontinuation.

10.3 Important Protocol Deviations

Important Protocol Deviations (IPDs) categories are defined by the study team before the first subject's visit and updated during the IPD reviews throughout the study prior to database lock. These definitions of IPD categories, sub-category codes, and descriptions will be used during the course of the study.

Eligibility deviations are defined in the protocol.

10.4 Demographic and Baseline Characteristics

All baseline tables will be summarized by the randomized treatment groups in Study 20120153. Baseline tables will summarize the following: demographics, cardiovascular medical history, laboratory parameters and background therapy.

10.5 Efficacy Analyses

Lipid parameters and their change and percent change from baseline will be summarized by scheduled visits, including LDL-C at Week 52. Descriptive statistics will be provided.

10.6 Safety Analyses

10.6.1 Analyses of Primary Endpoints

Adverse events will be coded using the latest version of Medical Dictionary for Regulatory Activities (MedDRA). Severity of AEs will be graded using the CTCAE ([Appendix B](#)) and recorded on the eCRF. All adverse event tables will be summarized by actual treatment group in Study 20120153.

Subject incidence of all TEAEs, serious TEAEs, and TEAEs leading to withdrawal of investigational product will be tabulated by system organ class, high level term and preferred term in descending order of frequency.

Subject incidence of device-related TEAEs will be tabulated by high level group term (including “administrative site reactions” and “device issues”) and preferred term in descending order of frequency.

Summaries of all TEAEs and serious TEAEs occurring in at least 1% of the subjects by preferred term in any treatment group will be provided in descending order of frequency.

Subject incidence of treatment emergent events of interest (EOIs) will be summarized according to the EOI search strategy categories defined by the EOI steering committee. The definition of each EOI may be modified and new EOI may be added based on findings from ongoing pharmacovigilance. Updates of the search strategy due to MedDRA upgrades or other reasons may not trigger a SAP amendment. However, the most recent EOIs per Amgen EOI search strategy will be used at the time of the analysis and these search terms will be included in an appendix of the study report. As of the date of preparing this version, the current EOI are:

- potential hypersensitivity events (based on narrow and broad search strategies)
- potential injection site reaction events (based on narrow and broad search strategies)
- potential muscle events (based on narrow and broad search strategies)
- potential neurocognitive events (based on high level group terms)
- potential hepatitis C infection (based on narrow and broad search strategies)
- transaminase elevations and potential hepatic disorders (based on narrow and broad search strategies)

Overall AE summary will be also be provided in subgroups specified in [Section 7.3](#).

10.6.2 Analyses of Exploratory Endpoints

Death, myocardial infarction, hospitalization for unstable angina, coronary revascularization, stroke, TIA, and hospitalization for heart failure will be adjudicated by an independent CEC. Non-coronary revascularizations will be collected on the eCRF and will not be adjudicated. Subject incidence of clinical events will be summarized by actual treatment group in Study 20120153.

10.6.3 Laboratory Test Results

Descriptive statistics will be provided for actual values and changes from baseline in select laboratory parameters at each protocol-specified scheduled visit. Laboratory analytes are provided in the protocol Table 1. Lab shift tables using the CTCAE v4.03 grading will be used for the select analytes of interest, when applicable.

In addition, CK and liver function test (LFT) abnormalities will be assessed by the incidence overall and by visits of the following categories:

- CK > 5 x ULN
- CK > 10 x ULN
- ALT or AST > 3 x ULN
- ALT or AST > 5 x ULN
- Total bilirubin \geq 2 x ULN
- (ALT or AST > 3 x ULN) and Total bilirubin > 2 x ULN and ALP < 2 x ULN

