6.1.4.2 Elevation of Liver Function Tests

Subjects with abnormal hepatic laboratory values (eg, alkaline phosphatase [ALP], AST, ALT, total bilirubin [TBL], or international normalized ratio [INR] or signs/symptoms of hepatitis may meet the criteria for withholding of IP, statin, and other applicable lipid background therapy. If the subject experiences an ALT or AST > 3X ULN, then they must be followed as detailed under section on close observation in [Appendix A](#).

IP, statin and other applicable lipid background therapy must be discontinued and the subject should be followed according to the recommendations in [Appendix A](#) (Additional Safety Assessment Information) for possible drug-induced liver injury (DILI), if ALL of the criteria below are met:

- TBL > 2x upper limit of normal (ULN) or INR > 1.5

AND

- AST or ALT > 3x ULN

AND

- no other cause for the combination of laboratory abnormalities is immediately apparent; important potential causes for abnormal AST/ALT or TBL values include, but are not limited to:
 - Obstructive gall bladder or bile duct disease
 - Viral or alcoholic hepatitis (eg, Hepatitis A/B/C/D/E, Epstein-Barr Virus, cytomegalovirus, Herpes Simplex Virus, Varicella, etc)
 - Progression of malignancy involving the liver (note that metastatic disease to the liver, by itself, should not be used as an explanation for significant AST/ALT elevations)
 - Hypoxic or ischemic hepatopathy or congestive hepatopathy in association with significant right sided heart failure
 - Concomitant administration of other hepatotoxins, including drugs that inhibit bilirubin glucuronidation (eg, indinavir, atazanavir, irinotecan) or herbal or dietary supplements
 - Heritable disorders causing impaired glucuronidation (eg, Gilbert's Syndrome); alpha-one antitrypsin deficiency
 - Autoimmune hepatitis
 - Nonalcoholic steatohepatitis (NASH) or other fatty liver disease

IP, statin and other applicable lipid background therapy should also be withheld and the subject should be evaluated for DILI if ANY of the following criteria are met:

- AST or ALT > 8x ULN at any time
- AST or ALT > 5x ULN but < 8x ULN for ≥ 2 weeks
- TBL > 3x ULN at any time

- ALP > 8x ULN at any time

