14. APPENDICES

Appendix A. Additional Safety Assessment Information

Adverse Event Toxicity Grading Scale

Refer to the NCI Common Terminology Criteria for AEs (CTCAE) Version 4.0 for AE grading and information. The CTCAE is available at the following link:

http://ctep.cancer.gov/protocolDevelopment/electronic_applications/ctc.htm.

When an AE cannot be graded by CTCAE v4.0 the following severity grade may be used:

Grade	Amgen Standard Adverse Event Severity Scoring System
1	MILD: Aware of sign or symptom, but easily tolerated
2	MODERATE: Discomfort enough to cause interference with usual activity
3	SEVERE: Incapacitating with inability to work or do usual activity
4	LIFE-THREATENING: Refers to an event in which the patient was, in the view of the investigator, at risk of death at the time of the event. (This category is not to be used for an event that hypothetically might have caused death if it were more severe.)
5	FATAL

Drug-induced Liver Injury Reporting & Additional Assessments

Reporting

To facilitate appropriate monitoring for signals of DILI, cases of concurrent AST/ALT and TBL elevation according to the criteria specified in [Section 6.1.4.2](#) (3x ULN for AST/ALT and 2x ULN for TBL) require the following:

- The event should be reported to Amgen as a serious adverse event within **24 hours** of discovery or notification of the event (ie, before additional etiologic investigations have been concluded)
- The appropriate eCRF (eg, adverse event eCRF) that captures information necessary to facilitate the evaluation of treatment-emergent liver abnormalities should be completed.

Other events of hepatotoxicity and potential DILI should be reported as serious adverse events if they meet the criteria for a serious adverse event defined in [Section 9.2.1](#).

Additional Clinical Assessments and Observation

All subjects in whom IP is withheld due to potential DILI or who experience AST/ALT elevations >3x ULN should undergo a period of “close observation” until abnormalities return to normal or to the subject’s baseline levels. Assessments that should be performed during this period include:

- Repeat liver chemistries within 24-48 hours (ALT, AST, ALP, TBL); in cases of TBL >2x ULN or AST/ALT much greater than 3x ULN, retesting should be performed within 24 hours

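### Does the SAP's laboratory reporting fall short because its only combined liver row carries an ALP limit and no table counts LDL-C below 25 mg/dL?

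*SAP*

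**What the plan says.** **Liver.** SAP 10.6.3 lists six categories, each reported overall and by visit: CK above 5 and above 10 times ULN, ALT or AST above 3 and above 5 times ULN, total bilirubin at or above 2 times ULN, and one combined category, "ALT or AST > 3 x ULN) and Total bilirubin > 2 x ULN and ALP < 2 x ULN".

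Protocol 6.1.4.2 describes possible drug-induced liver injury by three conditions that must all hold: AST or ALT above 3 times ULN, "TBL > 2x upper limit of normal (ULN) or INR > 1.5", and "no other cause for the combination of laboratory abnormalities is immediately apparent". Obstructive gall bladder or bile duct disease heads its list of other causes. ALP has a threshold there only as a separate trigger, "ALP > 8x ULN at any time".

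Protocol Appendix A refers back to 6.1.4.2. It restates the laboratory thresholds as 3 times ULN for the transaminases and 2 times ULN for bilirubin, and asks that such concurrent elevations be reported as serious adverse events within 24 hours, "before additional etiologic investigations have been concluded". SAP 10.6.1 tabulates serious treatment-emergent events and has an event-of-interest category for transaminase elevations and hepatic disorders.

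**LDL-C.** Protocol 7.2.1.5 and 7.2.2.4 both state that subjects are monitored for LDL-C below 25 mg/dL. The endpoint lists (protocol 10.1.1 to 10.1.4, SAP 4.1) contain LDL-C at week 52, and change and percent change in LDL-C by visit. They contain no count below a level. SAP 8 and 10.5 plan by-visit summaries. SAP 10.1 names the statistics: number of subjects, mean, median, SD or SE, minimum and maximum.

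**The concern.** The study plans no inference, so its tables are its findings, and laboratory values are a named safety endpoint. A subject with ALT 4 times, bilirubin 2.5 times and ALP 2.5 times ULN crosses the protocol's two laboratory thresholds but is missing from the SAP's only combined row. That row could read zero while such cases exist. The SAP gives no reason for the ALP limit, and Appendix A wants the report before the cause is known. The SAP also does not say whether the combined values must come from one sample, although Appendix A asks sites to "Repeat liver chemistries within 24-48 hours (ALT, AST, ALP, TBL").

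For LDL-C, a level singled out twice for monitoring would seem to deserve a count. A minimum shows that someone fell below 25 mg/dL, not how many did. By-visit tables keep one record per window (SAP Appendix A), so they also cannot show how many subjects were ever below it. If these were real omissions, a reader could come away with too favourable a picture of liver safety and no picture of very low LDL-C.

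**Working it through.** **Denominator.** Protocol 10.2: 950 × 0.75 × 0.9 = 641.25, rounded up to 642. The planned figure reproduces.

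**Step 1: what the ALP limit removes.** Take ALT 4 times and bilirubin 2.5 times ULN and vary ALP.

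| ALP (× ULN) | Combined row as planned | Same row without ALP limit |
|---|---|---|
| 0.9 | counted | counted |
| 1.9 | counted | counted |
| 2.0 | not counted | counted |
| 2.5 | not counted | counted |
| 8.5 | not counted | counted |

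The planned row is a subset of the wider one, and its label says so.

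**Step 2: where the removed subject still appears.** Let a be the number of subjects with ALT or AST above 3 times ULN, b the number with bilirubin at or above 2 times ULN, c the planned combined count, and K the number with ALT/AST above 3 and bilirubin above 2 times ULN at any ALP. Bilirubin above 2 implies bilirubin at or above 2, so every subject in K is also in a and in b. Hence c ≤ K ≤ min(a, b).

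For illustration, with assumed a = 10 and b = 6, K lies between c and 6. If a or b is zero, K is zero. The tables do not fix K in general, but they hide neither of the two elevations.

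**Step 3: whether the protocol's own cases are lost.** The 6.1.4.2 criterion is not simply the row without the ALP limit. It adds an INR route and the condition on other causes, and INR is not in protocol Table 1. Neither laboratory row reproduces it. Cases meeting the criterion are counted through the serious-event report in Appendix A, which has no ALP filter, and from there in the serious-event table of SAP 10.6.1. A narrower laboratory category that leaves out raised ALP is compatible with a criterion that sets aside cases with another evident cause, biliary obstruction first among those listed.

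**Step 4: sample timing.** ALT, AST, bilirubin and ALP all belong to the one chemistry panel in protocol Table 1. SAP Appendix A selects one record per visit window. For the by-visit row, values from the same draw are therefore the natural reading. The Appendix A retest sentence concerns follow-up of the subject. For bilirubin above 2 times ULN it goes on to ask for retesting within 24 hours, so it supplies no 48-hour pairing rule for these cases.

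**Step 5: LDL-C.** With 642 measured values, the median is the mean of the 321st and 322nd ordered values. If minimum < 25 ≤ median, between 1 and 321 subjects are below 25 mg/dL (1/642 = 0.16% to 321/642 = 50%). That range ignores the mean and SD and pools the groups, whereas SAP 10.1 summarizes by parent-study treatment group.

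The documents give no LDL-C distribution, so any closer figure is assumed. The normal share is Φ((25 − m)/s). For a lognormal with the same mean m and SD s, v = ln(1 + (s/m)²), the share is Φ((ln 25 − ln m + v/2)/√v), and the median is m/√(1 + (s/m)²).

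| Assumed mean, SD | Normal: below 25 | Lognormal: below 25 | Medians |
|---|---|---|---|
| 60, 20 | 4.0% (26) | 0.6% (4) | 60 and 56.9 |
| 50, 25 | 15.9% (102) | 10.9% (70) | 50 and 44.7 |
| 40, 30 | 30.9% (198) | 35.6% (228) | 40 and 32.0 |

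The two shapes differ in their medians, and the median is a planned statistic, so these pairs do not show that the planned table leaves the count open by that much. In the last line the normal shape also puts Φ(−40/30) = 9% of subjects below zero, which is impossible. What remains is that none of the listed statistics is a count.

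**The case for a change.** The strongest case for the concern is that serious-event and event-of-interest tables count reported terms, while laboratory values are a separate endpoint. A laboratory table should therefore show concurrent elevations without relying on site reporting. The ALP limit is unexplained, and in 642 subjects single cases matter: at an assumed true rate of 0.1% the chance of seeing at least one is 1 − 0.999^642 = 47%, and at 0.2% it is 72%. One subject removed by the limit could make the row read zero. The data are already collected, so extra rows would cost little.

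The facts in this stand. The planned row is a lower bound for the wider count. The SAP does not explain the ALP limit or state a timing rule. No output counts subjects below 25 mg/dL. A subject with an evident biliary cause may also fall outside the serious-event rule, because that rule refers back to 6.1.4.2.

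What does not follow is that the plan is wrong. A zero in a row whose label includes the ALP limit is a true statement about that category. Laboratory values as an endpoint are covered by actual values, changes from baseline and CTCAE shift tables for selected analytes, together with the threshold rows. Low cost does not turn a preferred table into a missing one.

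**Conclusion.** The concern does not hold. Followed as written, the plan gives correct and correctly labelled results. The combined row is a legitimate narrower category. Each elevation it leaves out is counted in a single-analyte row, and cases meeting the protocol's liver-injury criteria reach the serious-event tables regardless of ALP. LDL-C below 25 mg/dL is a monitoring statement, in no endpoint list and tied to no promised output.

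No endpoint, analysis set, denominator or conclusion is affected. The size of the supposed liver shortfall cannot be derived from the documents; the planned tables bound the concurrent count by c ≤ K ≤ min(a, b). The number of subjects below 25 mg/dL cannot be derived either. The conclusion assumes that sites report liver cases as Appendix A requires and that the combined row is printed with its full label. A row without the ALP limit or a count below 25 mg/dL could be informative, but their absence is a choice of presentation.

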10.6.4 Vital Signs

Vital signs will be summarized using descriptive statistics at each scheduled visit.

10.6.5 Exposure to Investigational Product

Descriptive statistics will be produced to describe the patient-month exposure to investigational product, the categorical representation of dose received, and the total quantity of oral IP used by randomized treatment group in Study 153.

Exposure definitions are provided in [section 6.3](#).

10.6.6 Exposure to Concomitant Medication

The number and proportion of subjects receiving the medications of interest (MOI) will be summarized by preferred term for each randomized treatment group in Study 20120153 as coded by the World Health Organization Drug (WHODRUG) dictionary.

11. Appendices

